Protocol Number: 17-MAN-001	Version Number: 1.1	Effective:12/21/17	Page: 5 of 13

Acronyms and Definitions:

NERHC – New England Regional Headache Center

Manistee Partners:		Title: CLINICAL STUDY PROTOCOL	
Protocol Number: 17-MAN-001	Version Number: 1.1	Effective:12/21/17	Page: 6 of 13

1. PURPOSE OF STUDY AND BACKGROUND

- a. Purpose: To assess the efficacy and safety of a topical prostaglandin F2 alpha analog (bimatoprost) applied to the fingernail bed in reducing frequency, severity, duration and disability of migraine headaches.
- b. Background: This study is important because it is estimated that 36 million people in the United States suffer from migraine headaches and this number may reach 1.2 billion worldwide. The global migraine evaluation survey found a 12% migraine prevalence worldwide and many patients suffer without adequate short-term treatment and/or long-term control (1). The annual value of loss productivity from migraine headaches in the United States is \$13 billion (1).

Prostaglandins are created from arachidonic acid and are part of the body's inflammatory response. They participate in a wide range of functions, such as contraction and relaxation of small smooth muscles, dilation and constriction of blood vessels, control of blood pressure and modulation of inflammation. Intravenous infusion of vasodilating prostaglandins (E2, E3, I2 and D2) has been shown to induce headaches, whereas non-vasodilating prostaglandins (F2 alpha) are not associated with headaches (2).

Hall, et al. (3) observed that treatment with topical prostaglandin F2 alpha analogs (applied either to the eye or fingernail bed) significantly reduced the frequency, severity and duration of headaches in migraine sufferers, as well as the migraine disability assessment score (MIDAS).

- c. Primary endpoint of the study: Does topical bimatoprost (a prostaglandin F2 alpha agonist) applied to the fingernail beds reduce the number of headache days per month in episodic migraineurs?
- d. Secondary endpoints: Does topical bimatoprost applied to the fingernail beds of episodic migraineurs (a) reduce severity of migraine headaches; (b) reduce duration of headaches; (c) improve the quality of life as measured by the MIDAS score and headache intensity assessment.

2. STUDY DESIGN

Study drug: Topical bimatoprost 0.03% solution is a prostaglandin F2 alpha analog. It is FDA approved for topical application to the eye in the treatment of glaucoma. Prostaglandins, including bimatoprost, have been used to topically treat glaucoma_for 30+ years. When applied to the eye, bimatoprost is well tolerated and results in decreased intraocular pressure. Eye drop application can be associated with alteration in pigmentation of pigmented tissues and

Manistee Partners:		Title: CLINICAL STUDY PROTOCOL	
Protocol Number: 17-MAN-001	Version Number: 1.1	Effective:12/21/17	Page: 7 of 13

eyelash growth. It is rarely associated with intraocular inflammation, macular edema, bacterial keratitis, conjunctival hyperemia, conjunctival hemorrhage, eye irritation, eye pain, itchy eye, erythema of the eyelid, eyelid itchiness, instillation site irritation, punctate keratitis, visual blurring and visual acuity reduction. Eye drop application has also been associated with periorbital and lid changes including deepening of the eyelid sulcus (4). Topical application to the fingernail bed may be associated with a slight increase in fingernail growth.

Headaches (but not the more severed and debilitating frequent migraine headaches) are reported as a potential systemic adverse side effect in 1-5% of patient's taking topical bimatoprost ophthalmic solution administered to the eye (4). Headaches may rarely occur with many medications. However, the greater than 80% positive response rate with reduction in headache frequency and severity documented in the study by Hall, et al. (3) using topical bimatoprost to the fingernails represents a significantly greater benefit without meaningful added risk to study patients.

- a. Study treatment group: This will be a 16-week double-blind, randomized, placebo-controlled parallel group trial of prophylactic bimatoprost in up to 80 patients with episodic migraine. There will be a 1:1 randomization across the two groups, bimatoprost and placebo. Randomization will be done using a computer random number generator. Randomization assessment of the subjects will be done blind to treatment assignment. Based on a review of placebo-control trials of migraine, we assume a 20% difference in changes from baseline in monthly headache frequency for a calculation of sample size. With a power of [80%, significance of this level of 5% (one-sided) and an effect size of 0.8 (large), the sample size requirement is 30 in each group.
- b. Treatment regimen: Bimatoprost 0.03% solution and a placebo will be placed in ophthalmic bottles. Treatment and placebo groups will place one drop (approximately 25 μl) once daily on the nail bed (lunula) of each of four fingers on the non-dominant hand. The drops will be allowed to air dry. No nail polish is to be used during the trial. This compares to one drop (approximately 25 μl) of 0.03% solution being FDA- approved for administration once daily into each of two eyes for treatment of glaucoma.
- c. Study visits: The study will consist of four visits for each patient: a screening visit (V1), week -4; randomization visit (V2), week 0; a compliance visit (V3), week 6; an end-point visit (V4), week 12. A compliance phone call assessment will be made to each participant at week 3 and week 9.
- d. Study duration: The study will continue for 16 weeks and each participant will be expected to participate in the full extent of the study.

Manistee Partners:		Title: CLINICAL STUDY PROTOCOL		
Protocol Number: 17-	MAN-001	Version Number: 1.1	Effective:12/21/17	Page: 8 of 13

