3. CRITERIA FOR SUBJECT SELECTION

- a. Number of subjects: Eighty subjects are expected to participate.
- b. Gender of subjects: Male and female patients will be admitted to the study. There will be no gender restriction, except pregnant and lactating females will be excluded.
- c. Age of subjects: The age range will be 18-65 years. Migraine manifestation and treatment is more complex and variable in children and adolescents. General medical issues and transportation availability can become problematic for people over age 65. Therefore, the age range of 18-65 has been selected.
- d. Racial and ethnical profile: There are no restrictions based on race or ethnic origin.
- e. Inclusion criteria: Inclusion for study will be diagnosis of episodic migraines based on International Classification of Headache Disorders (ICHD) II criteria and experiencing headaches for 4-14 days per month, the internationally accepted definition of "episodic migraine" patients. All our patients will be screened to make sure they do not have other medical conditions that are causing their migraines. The subjects in the study will already be taking medications as recommended by their primary physician. Patients will be permitted to use stable doses of up to three different standard migraine preventive drugs for at least three months before study onset. Patients will be allowed to treat acute migraine headaches as usual and they must show compliance (at least 80%) with a headache diary during the four-week run-in phase.
- f. Exclusion criteria: Exclusion criteria are significant liver or renal dysfunction, on treatment for inflammatory bowel disease, medication over-use for headaches according to the ICHD II criteria, use of antipsychotics in the past month, recent (in the past six months) history of alcohol or drug abuse, allergy to bimatoprost and its compounds, severe comorbid psychiatric illness, severe infection, malignancy, severe cardiovascular disease, neurodegenerative disorders, pregnancy and lactation, and sexually active women of child bearing age who do not use any method of contraception.
- g. Vulnerable subjects will not be included

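### The inputs stated in Protocol section 2.a give 20 to 21 patients per group, not the stated requirement of 30

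*Protocol*

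**What the plan says.** Protocol section 2.a describes a two-group parallel trial in at most 80 patients: "There will be a 1:1 randomization across the two groups, bimatoprost and placebo". For the sample size it first says "we assume a 20% difference in changes from baseline in monthly headache frequency for a calculation of sample size". It then sets power at 80% and gives the error rate, the standardised effect and the result in one run: "significance of this level of 5% (one-sided) and an effect size of 0.8 (large), the sample size requirement is 30 in each group". Section 3.a adds: "Eighty subjects are expected to participate". At 1:1 that is 40 per group.

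Section 2.a names no test, gives no standard deviation and does not say whether 30 means randomised or evaluable patients. The calculation mentions no allowance for attrition, for a rank test or for the interim analysis that section 4.g foresees.

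**The concern.** A standardised effect, a one-sided significance level, a power and an allocation ratio together determine the size of a two-group comparison of means. No standard deviation is needed. Section 2.a gives all four and then a result that looks about half as large again as it should be.

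This sentence is the protocol's only sample-size justification. If its result does not follow from its inputs, at least one input is not the one used, or a step has been left out. The reader then cannot tell which effect the trial was planned to detect, or with what power. That matters most if recruitment falls short: the 80 in section 2.a is a ceiling, so 30 per group is the only stated figure that can serve as a minimum.

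**Working it through.** **Inputs, all from Protocol section 2.a:** allocation 1:1; standardised effect d = 0.8; one-sided alpha 0.05 (z = 1.6449); power 0.80 (z = 0.8416). Target to reproduce: 30 per group.

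**Normal formula.** n per group = 2 × ((z for alpha + z for power) / d)²
= 2 × ((1.6449 + 0.8416) / 0.8)²
= 2 × (3.1081)²
= 19.32, so 20 per group.

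**Exact two-sample t-test (noncentral t).** n = 20.03, so 21 per group.

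The figure of 30 is not reproduced. The excess over the t-test result is 30 − 21 = 9 per group, and 9/21 = 43%.

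**Power on the stated inputs** (t-test, one-sided 5%, d = 0.8):

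| n per group | Power |
|---|---|
| 20 | 79.9% |
| 21 | 81.7% |
| 30 | 92.2% |
| 40 | 97.1% |

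**Could one unstated step account for 30?** At d = 0.8:

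- Two-sided 5% at 80% power: 25.52, so 26. This is still not 30, and it contradicts the stated sidedness.
- Rank test at its lowest possible large-sample efficiency relative to the t-test (0.864), one-sided: 20.03 / 0.864 = 23.19, so 24.
- Attrition alone, starting from 21 evaluable and dividing by the retained fraction: 1 − 21/30 = 30% loss.

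**What does give 30?** Only changed or added inputs, and several of them do:

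- One-sided 5%, 80% power, d = 0.65: n = 29.97, so 30.
- One-sided 5%, d = 0.8, 92% power: n = 29.77, so 30.
- Two-sided 5%, d = 0.8, 85% power: n = 29.05, so 30.
- One-sided 5%, d = 0.8, 80% power, 30% attrition: 21 / 0.70 = 30.

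**Why the choice matters.** If d = 0.65 was intended, power at one-sided 5% is 66% with 21 per group, 80.0% with 30 and 89.2% with 40. If d = 0.8 was intended, 21 per group already suffices.

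The assumed 20% difference offers no other route to 30, because without a standard deviation it cannot be converted to a standardised effect.

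**The case against.** The strongest reply is that the consequence is small. The stated 30 is more than the inputs require, and expected enrolment is higher still. On the stated inputs the trial is not underpowered, and correcting the sentence changes no patient number and no test. Even if d = 0.65 was the real target, 40 per group gives 89% power. All of this stands and limits the weight of the point. The 89% and 97% figures do assume that all 80 patients are enrolled and none is lost, which section 2.a, giving 80 as an upper limit, does not promise.

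A second reply is that 30 may be poorly reported rather than miscalculated. Explanations can be combined: the worst-case rank-test figure of 24 with 20% attrition gives 24 / 0.80 = 30. The 30% attrition figure also depends on where one starts; from 20 per group it is 1 − 20/30 = 33%. That is fair, and it means the cause cannot be identified from outside. But every such route needs at least one input that section 2.a does not state, and the combined route needs two. The sentence presents 30 as following from the listed inputs, and it does not.

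A third reply is that a fuller derivation may sit in a statistical analysis plan. It might explain the number, but it would not make the protocol's own sentence correct.

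Finally, offering model wordings may invite an input chosen afterwards to fit 30. That caution is sound: the sponsor should report what was actually used.

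**Conclusion.** The point holds. On its own inputs, section 2.a should give 20 per group (normal formula) or 21 (t-test), and 30 per group carries 92.2% power rather than 80%. The stated requirement is 9 per group, or 43%, above the t-test result.

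This rests on reading 0.8 as a standardised mean difference, which the label large supports, and on a comparison of two means with 1:1 allocation. It does not depend on choosing the normal formula or the t-test, nor on the stray bracket printed before the power figure, which may come from the reading of the PDF.

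The error is conservative if d = 0.8 is intended and does not threaten the trial's validity. It should still be corrected, because the document leaves open whether the design target is d = 0.8 at 92% power, d = 0.65 at 80% power, or something else.

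**What to change.** Restate the sample-size sentence in section 2.a with the inputs actually used, the test assumed, whether the figure counts evaluable or randomised patients, and the power that results. If the stated inputs stand, the sentence should say that 21 evaluable patients per group give 80% power and that 30 per group give 92%.

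If 30 came from something else, name it. Examples of a consistent statement, all one-sided 5%:

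- d = 0.65, 30 per group for 80% power;
- d = 0.8, 30 per group for 92% power;
- d = 0.8, 21 evaluable per group for 80% power, with 30 randomised to allow for 30% attrition.

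These illustrate the form only. The sponsor should report the original assumption, not pick the one that fits.

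The cost is one reworded sentence. None of these versions needs more than 30 per group, which is below the 40 per group expected, so no patients are added.

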3. CRITERIA FOR SUBJECT SELECTION

- a. Number of subjects: Eighty subjects are expected to participate.
- b. Gender of subjects: Male and female patients will be admitted to the study. There will be no gender restriction, except pregnant and lactating females will be excluded.
- c. Age of subjects: The age range will be 18-65 years. Migraine manifestation and treatment is more complex and variable in children and adolescents. General medical issues and transportation availability can become problematic for people over age 65. Therefore, the age range of 18-65 has been selected.
- d. Racial and ethnical profile: There are no restrictions based on race or ethnic origin.
- e. Inclusion criteria: Inclusion for study will be diagnosis of episodic migraines based on International Classification of Headache Disorders (ICHD) II criteria and experiencing headaches for 4-14 days per month, the internationally accepted definition of "episodic migraine" patients. All our patients will be screened to make sure they do not have other medical conditions that are causing their migraines. The subjects in the study will already be taking medications as recommended by their primary physician. Patients will be permitted to use stable doses of up to three different standard migraine preventive drugs for at least three months before study onset. Patients will be allowed to treat acute migraine headaches as usual and they must show compliance (at least 80%) with a headache diary during the four-week run-in phase.
- f. Exclusion criteria: Exclusion criteria are significant liver or renal dysfunction, on treatment for inflammatory bowel disease, medication over-use for headaches according to the ICHD II criteria, use of antipsychotics in the past month, recent (in the past six months) history of alcohol or drug abuse, allergy to bimatoprost and its compounds, severe comorbid psychiatric illness, severe infection, malignancy, severe cardiovascular disease, neurodegenerative disorders, pregnancy and lactation, and sexually active women of child bearing age who do not use any method of contraception.
- g. Vulnerable subjects will not be included
- h. Consent: All subjects will read and sign the appropriate form approved by the Asentral Review Board (IRB). This study will be conducted in accordance with the principles of Good Clinical Practice and with the US Food and Drug Administration (FDA) guidelines for safety monitoring, as well as the last revisions of the Declaration of Helsinki. The study will also be registered in www.clinicaltrials.gov.
- i. Subject Identification Number: Before subjects begin participation in any study-specific activities/procedures, Manistee requires a copy of subject information. Each subject who enters into the screening period for the study shall sign and date the informed consent and receive a unique, randomly assigned subject identification number. The subject identification number will be used to identify the subject

Manistee Partners:		Title: CLINICAL STUDY PROTOCOL	
Protocol Number: 17-MAN-001	Version Number: 1.1	Effective:12/21/17	Page: 9 of 13

throughout the clinical study and will be used on all study documentation related to that subject.

A subject is considered enrolled when the Principle Investigator or Sub-Investigator decides that the subject has met all eligibility criteria and is randomized. The Principle Investigator or Sub-Investigator is to document this decision date and enter it in the subject's medical record and on the enrollment case report form (CRF).

The subject identification number will remain constant throughout the entire clinical study; it will not be changed after initial assignment, including if a subject is rescreened. This number will not include any identifiers for the subject.

4. METHODS AND PROCEDURES

- a. Study Drug: The study drug will be sourced, labeled, and packaged in 3 ml sterile ophthalmic bottles by Boulevard Compounding Pharmacy, a licensed pharmacy, located in Worcester, Massachusetts. It will be stored there at room temperature in a locked cabinet until needed for distribution at the clinical test site. The pharmacy will label each bottle with a unique number, assigned to a unique subject identification number, according to the Sponsor's computer-generated randomization code. The study site will be responsible for recording the study drug code on each subject's case report form.
- b. Study Visits and Duration: The study will be a 16-week double-blind, randomized placebo-control parallel-group trial of prophylactic bimatoprost in patients with migraine. The study will consist of a 4-week baseline after which the patients will be treated for 12 weeks. The patients will come in four visits: a screening visit (V1), week -4; a randomization visit (V2), week 0; a compliance visit (V3), week 6; an end-treatment visit (V4), week 12. Compliance phone call assessments will be made to each participant at week 3 and week 9.
 - i. The screening visit (V1) will consist of informed consent, eligibility and exclusion criteria, medical and psychiatric history, concomitant medications, height, weight, vital signs, physical and neurological examination, review of daily diary and dispensing of diaries. Urine tests for drug use, blood sampling for blood chemistries and EKG will be performed.
 - ii. The randomization visit (V2) consists of diary collection, diary review and, where necessary, correction by the subject, health status changes, concomitant medications, MIDAS questionnaire, dispensing of daily diaries and study medication. At the end of the randomization visit, but before medication is dispensed, it will be established that the subject meets eligibility and exclusion criteria.

Manistee Partners:		Title: CLINICAL STUDY PROTOCOL	
Protocol Number: 17-MAN-001	Version Number: 1.1	Effective:12/21/17	Page: 10 of 13

- iii. The compliance visit (V3) consists of diary collection and review and, when necessary, correction by the subject, study medication accountability, medication administration compliance, health status changes, adverse occurrences, concomitant medications and dispensing of study medication as necessary.
- iv. The end treatment (V4) consists of diary and study medication collection, diary review and, where necessary, correction by the subject, study medication accountability, medication administration compliance, health status changes, adverse event occurrences, concomitant medications, and MIDAS questionnaire.
- v. The week 3 and week 9 phone calls will be made to each participant to confirm compliance with medication usage, diary completion, health status changes, adverse medical events, and concomitant medications will be addressed.
- c. Data analysis and data monitoring: Patients will be instructed to record in a diary the number of headache attacks per day and the headache intensity, duration, disability level, associated symptoms and medications taken. The headache diary will be filled out every day of the month, even on days when the patient has no headache (see diary form).
 - The Migraine Disability Assessment Scale (MIDAS) is a five-item instrument developed to measure migraine related disability and functional consequences. It is divided into four categories based on the score of: 0-5, minimal disability; 6-10, mild disability; 11-20, moderate disability; greater than 20; severe disability. Reliability and validity of MIDAS questionnaires have been well established
- d. Primary outcome: The primary outcome measures will be the difference in the average change from the 4-week baseline period in the number of migraine headache days with moderate or severe intensity compared to weeks 9-12 between the two groups.

A migraine headache day is defined as any calendar day on which a headache which meets criteria A, B and C listed below occurs.

- A. Headache has at least two of the following:
 - i. Unilateral location
 - ii. Pulsating quality
 - iii. Moderate or severe pain intensity
 - iv. Aggravated by or causing avoidance of routine physical activity (e. g., walking or climbing stairs)
- B. At least one of the following:
 - i. Nausea and/or vomiting
 - ii. Photophobia and phonophobia

Manistee Partners:		Title: CLI		
Protocol Number: 17-MA	N-001 Version Num	aber: 1.1 Effective:1	2/21/17 Page: 1	1 of 13

- iii. Typical aura (*i. e.,* visual, sensory, or speech/language) accompanying or iv. Within 60 minutes before headache begins
- C. Duration of headache lasting 2 hours or longer on a calendar day unless an acute, migraine-specific medication (*i. e.,* triptan or ergot derivative) was used after the start of the headache, in which case no minimum duration to be specified.
- e. Secondary outcomes: Secondary outcome measures will be:
 - i. Percentage reduction in the average weekly number of migraine headaches comparing baseline to weeks 9-12.
 - ii. Change in the MIDAS score comparing baseline to weeks 9-12.
 - iii. Change in severity of headaches comparing baseline to weeks 9-12.
 - iv. Change in duration of headaches comparing baseline to weeks 9-12
- f. Data recording: All data will be collected in the form of the written diaries and case report forms. No data will be collected electronically. All original data documents will be photocopied and provided to the Sponsor for data analysis. At the conclusion of the study all data documents will be scanned and converted into electronic files for secure archival storage; all the original paper documents will be stored in a locked cabinet.
- g. Data review and analysis: All study data will remain blinded to both the patients and all investigators at the NERHC. Manistee Partners will have access to unblinded data throughout the trial as it is accrued. Interim data analysis will be undertaken at a midpoint of the trial.
- h. Data storage and confidentiality: All data will be stored on a secure server in a secure file for a period of 5 years.
- i. Transition from research participation: At the termination of the study (V4), each subject will be returned to their usual care. There will be no compassionate use extension or rollover of placebo group to treatment group.

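### Section 4.g gives the sponsor running access to unblinded data, although the sponsor also analyses the paper records and the final size is open between 60 and 80

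*Protocol*

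**What the plan says.** Section 4.g keeps the data blinded to patients and to investigators at the headache center. It then gives Manistee Partners "access to unblinded data throughout the trial as it is accrued", and it plans an interim analysis around the middle of the trial. The access carries no restriction by role or purpose. Manistee Partners is read here as the sponsor because its name heads every page and section 3.i has it receiving subject information. The visible text does not say so outright.

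Four other places bear on this:

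- **4.f:** "All original data documents will be photocopied and provided to the Sponsor for data analysis". Collection is on paper only.
- **4.a:** the pharmacy numbers the bottles "according to the Sponsor's computer-generated randomization code", and "The study site will be responsible for recording the study drug code on each subject's case report form".
- **4.d:** the primary outcome has to be derived from diary entries: "A migraine headache day is defined as any calendar day on which a headache which meets criteria A, B and C listed below occurs".
- **2.a and 3.a:** the trial is a "16-week double-blind, randomized, placebo-controlled parallel group trial of prophylactic bimatoprost in up to 80 patients with episodic migraine"; under its power assumptions "the sample size requirement is 30 in each group"; and "Eighty subjects are expected to participate".

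**The concern.** The party given running arm-level access also receives every record for analysis, and the randomization code is its own. Two decisions that affect the result are then open to someone who can see the accumulating comparison.

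- **When to stop recruiting.** The three statements on size fit together as a minimum of 60 and a cap of 80, but no text fixes the final number or makes it independent of results.
- **How diary days are classified.** Each day must be judged against criteria A, B and C, including the waiver of minimum duration after migraine-specific acute medication. No party other than the sponsor is named as receiving the data.

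The evidence will be one comparison in 60 to 80 patients at one-sided 5%. If the p-value falls just below 0.05, nothing in the protocol lets a reader exclude that known results shaped the size or the coding. An interim boundary in the SAP would not cure this, because it governs a formal test and not day-to-day access. The absence of a boundary from the protocol is not part of this point.

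**Working it through.** **Inputs from the protocol.** One-sided 5%, 80% power, standardised effect d = 0.8, 1:1 allocation and 30 per group (2.a); up to 80 patients (2.a) and 80 expected (3.a); 12 weeks from randomisation to the last outcome (4.b).

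**The plan's own figure.** n per group = 2(1.645 + 0.842)²/0.8² = 19.3, so 20 (21 by t test). The stated 30 does not follow from the stated inputs. That is a separate matter and this point does not depend on it; 60 is used below only as the stated requirement.

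**Size and power with a fixed number.** With one final t test the one-sided error is 5% by construction at 60 or at 80 (simulated: 5.00% and 5.03%). Power at d = 0.8, from the noncentral t, is 92.2% with 30 per group and 97.1% with 40.

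**Route 1: steering where recruitment ends.** Assumptions: no treatment effect, a single final test, no early efficacy claim, and the most favourable stopping choice at every step (the worst case for error).

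- Let S_n be the cumulative score, with variance n.
- Recruitment may close at N = 60, 62, …, 80. L randomised patients then have no week-12 outcome yet, so N − L outcomes are known.
- The final test rejects if S_N > 1.645√N.
- Given S = s, the chance of rejecting after closing at N is 1 − Φ((1.645√N − s)/√L).
- Backward induction from N = 80 takes, at each step, the larger of this chance and the value of continuing.

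| Outcomes pending (L) | One-sided error | Check by simulated t tests |
|---|---|---|
| 10 | 6.22% | 6.23% |
| 20 | 5.83% | 5.83% |
| 30 | 5.61% | 5.60% |
| 40 | 5.45% | 5.44% |
| 50 | 5.31% | not run |
| 60 | 5.16% | not run |
| 70 | 5.05% | not run |

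For 50 or more pending, the number of known outcomes is N − L or zero, whichever is larger, and the root term is √(N − known). The simulations used 200,000 trials. The protocol gives no accrual rate. Ten pending means about 10 patients randomised per 12 weeks, so 80 would take 80/10 × 12 = 96 weeks; faster accrual moves down the table.

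If instead there is a single look at n₁ outcomes, and N = 60 or 80 is chosen by the larger conditional error 1 − Φ((1.645√N − s)/√(N − n₁)), the error is 5.52%, 5.70% or 5.98% for n₁ = 30, 40 or 50.

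**Route 2: arm-aware coding.** Assumption, not an estimate: coding moves the group difference by 0.02 to 0.05 SD in favour of treatment. The test statistic then has noncentrality shift × √(n/2), with n per group.

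- 30 per group (critical t 1.672): 0.02 × √15 = 0.077 gives 5.84%; 0.05 × √15 = 0.194 gives 7.30%.
- 40 per group (critical t 1.665): 0.02 × √20 = 0.089 gives 5.98%; 0.05 × √20 = 0.224 gives 7.73%.

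**The case against.** The best case for the protocol has five parts.

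- **Size.** Section 3.a expects 80, so 80 may simply be the target and cap. No text lets results decide the end of recruitment, and patients come from the blinded site's own files (6.a). This is a fair reading. What stands is that 80 is an expectation under a cap, and closing at 60 would breach nothing written.
- **Magnitude.** The top steering figure needs slow accrual together with perfect steering; with 70 outcomes pending the error is 5.05%. This is correct, and the figures should be read as upper limits.
- **Coding.** Patients keep the diary, review and correction by the subject take place at a blinded site, criteria A to C are fixed in advance, and the originals are kept, so recoding could be audited. These safeguards make a large shift less likely, and the 0.02–0.05 SD range has no basis in the document. They do not cover transcription and classification after the copies leave the site.
- **Role separation.** A SAP or data-management plan may name an outside analyst, and section 6.f says only that the sponsor pays for the statistical analysis. That is possible, but 4.g as written grants the access without restriction.
- **Blinding label.** Patients and investigators are blinded, so calling the trial double-blind is not a contradiction. Agreed; the point is the access itself, not the label.

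**Conclusion.** The concern holds as a cheap improvement. The exposure comes from a rule the protocol states, not from detail that a SAP would be expected to supply. The one-sided error is 5.0% if nothing follows from the access. It reaches at most 6.2% under worst-case steering of the size with 10 outcomes pending, and it falls towards 5% as more are pending. It would be 5.8–7.7% if coding shifted the difference by the assumed 0.02–0.05 SD. None of this shows that bias will occur. The main cost is credibility: a marginal result could not be defended against either route. The conclusion rests on reading Manistee Partners as the sponsor and on treating 60 to 80 as the permitted range. Confidence is medium.

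**What to change.** 1. **Sections 4.g and 4.a.** Replace the access sentence with: *Sponsor staff who decide on sample size or stopping, handle or code diary data, or do the final analysis stay blinded to treatment arm until the database is locked.* State in 4.a that the code is held until then by a party with none of these roles, for example the pharmacy, which already labels by it. The drug code may stay on the case report form, because without the list it does not reveal the arm.
2. **Sections 2.a and 3.a.** State one randomised number that does not depend on accrued results: the 80 already expected, with 60 as the minimum evaluable number if that is the intent.
3. **Section 4.g, interim analysis.** State that it uses pooled data or is done by someone with none of the roles in item 1. State also that it cannot change the size or support an efficacy claim unless a boundary pre-specified in the protocol or SAP holds one-sided 5% overall.

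**Cost.** Wording in four sections, and no enrolment beyond the 80 expected. Without an efficacy look there is no power cost. The sponsor gives up its running arm-level view and its informal flexibility over size. Any arm-level safety view would have to go through the code holder; the pharmacy has no stated safety-review role, so keeping such a view may need a further named person. An interim analysis by arm would also need someone outside these roles; a pooled one would not.
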